7.4.3 PROMIS Physical Function Scale

The PROMIS Physical Function Scale provided in [Appendix 1](#) is a 10-question PRO instrument that will be used to assess physical functioning based on use of the upper extremities (dexterity), lower extremities (walking or mobility), and central regions (neck, back) and on instrumental activities of daily living. Five questions address the degree to which the subject's health limits certain physical activities, and subjects select a response to each question that ranges from 1 ("cannot do") to 5 ("not at all"). Five questions address the degree to which the subject is able to perform certain physical activities, and subjects select a response to each question that ranges from 1 ("cannot do") to 5 ("without any difficulty").

7.4.4 Worst Stiffness Numeric Rating Scale

The Worst Stiffness NRS provided in [Appendix 2](#) is a single-item PRO instrument designed to assess "worst" stiffness at the site of the tumor. The instrument uses an 11-point NRS that ranges from 0 ("no stiffness") to 10 ("stiffness as bad as you can imagine"). Subjects are asked to recall their "worst" stiffness at the site of the tumor in the last 24 hours.

7.4.5 Brief Pain Inventory Short Form and Worst Pain Numeric Rating Scale

The BPI Short Form provided in [Appendix 3](#) is a PRO instrument used to evaluate the severity of a subject's pain and the impact of this pain on the subject's daily functioning ([Cleeland, 1994](#)). Subjects list current pain treatments and rate on a scale from 0 to 10 their worst, least, average, and current pain intensity; how much relief current pain treatments provide; and the degree to which pain interferes with general activity, mood, walking ability, normal work, relations with other people, sleep, and enjoyment of life.

The Worst Pain NRS is an item in the BPI that assesses a subject's "worst" pain in the last 24 hours. The 11-point NRS for this item ranges from 0 ("no pain") to 10 ("pain as bad as you can imagine").

7.4.6 EQ-5D-5L

The EQ-5D-5L assessment provided in [Appendix 4](#) is a widely used PRO quality-of-life instrument developed by the EuroQol Group that consists of 2 pages: the EQ-5D descriptive system and the EQ VAS. The descriptive system comprises 5 dimensions (mobility, self-care, usual activities, pain/discomfort, and anxiety/depression), and subjects select one of 5 levels (statements describing severity) that most accurately describes their health state for each dimension. The VAS records the subject's self-rated general health on a vertical VAS.

7.5 Pharmacokinetic and Pharmacodynamic Assessments

Serum will be collected and optional synovial fluid may be collected to assess AMB-05X, CSF1, and anti-AMB-05X antibody at the visits indicated in the Schedule of Events.

Serum AMB-05X and CSF1 concentrations will be measured at the following visits:

- Day 1, Week 4, and Week 8: before dosing and within 15 minutes after the end of infusion
- Weeks 2 and 6:
 - If the subject will receive study drug at the visit, collect the serum sample before dosing.
 - If the subject will not receive study drug at the visit, collect the serum sample at any time during the visit.
- Week 10:
 - If the subject will receive study drug at this visit, collect serum samples before dosing and within 15 minutes after the end of infusion.
 - If the subject will not receive study drug at this visit, collect a serum sample at any time during the visit.
- Weeks 12, 14, and 24: at any time during the visit

Synovial AMB-05X and CSF1 concentrations may be measured pre-dose at Day 1 and pre-dose at the visit associated with the last dose of study drug for each subject (Week 8 or Week 10) as an optional assessment.

ADA levels against AMB-05X will be measured from pre-dose serum samples and any synovial samples collected at Day 1, at Week 4, at the visit associated with the last dose of study drug for each subject (Week 8 or Week 10), and at Week 14.

Actual dosing and sampling times will be accurately recorded on the eCRF.

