2.3.2 Pharmacokinetics

Single IV doses of AMB-05X administered to cynomolgus monkeys produced a nonlinear increase in exposure at doses of 0.1 to 5 mg/kg but an approximately dose-proportional increase at doses of 5 to 100 mg/kg. When receptor-mediated clearance had been saturated at higher serum concentrations of AMB-05X (████ μg/mL), the kinetics of AMB-05X became linear. The volume of distribution at steady state for AMB-05X in monkeys was approximately equal to plasma volume, indicating limited extravascular distribution.

The toxicokinetics of repeated IV doses of AMB-05X was assessed in both 4-week and 14-week repeat-dose toxicity studies and did not differ markedly between male and female monkeys. In general, exposure to IV AMB-05X increased approximately dose proportionally in monkeys over the dose range of 10 to 300 mg/kg. No marked (>2-fold) accumulation of AMB-05X was observed after 4 or 13 once-weekly doses in monkeys. During the dosing phase of these studies, AMB-05X-binding ADAs were detected in 1 of 30 animals in the 4-week study and 13 of 35 animals in the 14-week study; during the recovery phase of the 14-week study, ADAs were detected in 8 of 10 animals. In general, ADAs decreased exposure to AMB-05X in these animals. For both studies, high concentrations of AMB-05X in the serum samples may have interfered with detection of ADAs in animals that tested ADA-negative.

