3.2.2 Pharmacokinetic and Pharmacodynamic Secondary Endpoints

- Serum (and optional synovial) AMB-05X levels
- Serum (and optional synovial) AMB-05X–binding ADA levels
- Serum (and optional synovial) CSF1 levels

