8.9 Follow-up Visit 9 (Week 14 ± 3 Days)

- Record any changes in concomitant medications since the previous visit.
- Record any new AEs that may have occurred since the previous visit and follow up on the status of any existing AEs.
- Obtain weight.
- Measure vital signs (blood pressure, heart rate, temperature, and respiratory rate) with subject in a sitting position after having rested for 5 minutes.
- Conduct a full physical examination and document any changes since the previous visit.
- Evaluate ROM of the affected joint.
- Administer the Worst Stiffness NRS.
- Collect a urine sample for a urine pregnancy test for female subjects of childbearing potential and for urinalysis.
- Collect blood samples for clinical laboratory (chemistry and hematology).
- Collect blood samples for serum PK, CSF1, and anti-AMB-05X antibody.
- Schedule the next visit with the subject.
- Contact IWRs to record the visit.

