8.10 Follow-up Visit 10 (Week 24 ± 7 Days)

- Record any changes in concomitant medications since the previous visit.
- Record any new AEs that may have occurred since the previous visit and follow up on the status of any existing AEs.
- Obtain weight.
- Measure vital signs (blood pressure, heart rate, temperature, and respiratory rate) with the subject in a sitting position after having rested for 5 minutes.
- Conduct a full physical examination and document any changes since the previous visit.

- Evaluate ROM of the affected joint.
- Administer the following PRO instruments:
 - PROMIS Physical Function Scale
 - Worst Stiffness NRS
 - BPI Short Form
 - EQ-5D-5L
- Collect a urine sample for a urine pregnancy test for female subjects of childbearing potential and for urinalysis.
- Collect blood samples for clinical laboratory tests (chemistry and hematology).
- Collect blood samples for serum PK and CSF1.
- Perform MRI. A central radiologist will evaluate MRI scans to assess tumors.
- Contact IWRS to record the visit.

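### The last ADA test is at Week 14 although serum is drawn at Week 24, so ADA first detectable after Week 14 is missed

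*Combined protocol and SAP*

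**What the plan says.** Section 3.2.2 lists serum (and optional synovial) AMB-05X-"binding ADA levels" among the secondary endpoints. Section 7.5, repeated in the Section 1.1 synopsis, sets the ADA samples at Day 1, Week 4, and then "at the visit associated with the last dose of study drug for each subject (Week 8 or Week 10), and at Week 14".

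The two follow-up visits differ on this point. At Visit 9 (Week 14), Section 8.9 says "Collect blood samples for serum PK, CSF1, and anti-AMB-05X antibody". At Visit 10 (Week 24), Section 8.10 says only "Collect blood samples for serum PK and CSF1". Drug and CSF1 levels are measured at both visits; Section 7.5 gives their timing as "Weeks 12, 14, and 24: at any time during the visit". No reason is given for leaving ADA out at Week 24.

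On the animal experience, Section 2.3.2 reports ADA during dosing in "13 of 35 animals in the 14-week study" and in 8 of 10 animals in that study's recovery phase. It adds that "high concentrations of AMB-05X in the serum samples may have interfered with detection of ADAs in animals that tested ADA-negative".

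**The concern.** Antibodies to a biologic can become detectable after dosing stops, either because they form late or because falling drug levels unmask them. A schedule that ends at Week 14 sees neither after that date. The follow-up period runs ten weeks longer, and blood is already taken at its end.

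What is at stake is the completeness of one secondary endpoint. If some subjects turn positive between Week 14 and Week 24, the reported ADA incidence understates the true one, and the Week 24 drug and CSF1 levels have to be read without knowing ADA status at that visit. The primary endpoint and the escalation rules do not depend on ADA.

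**Working it through.** The plan states no ADA rate, human half-life, Week 14 concentration or assay drug tolerance, so there is no figure of its own to reproduce. Three checks were made.

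**1. Time from last dose to last sample** (study days and windows from Section 1.3, dosing weeks from Section 4.1.2)

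- Every 2 weeks: last dose Week 10 = Day 71. Week 14: 99 - 71 = 28 days (22 to 34 with visit windows). Week 24: 169 - 71 = 98 days (88 to 108).
- Every 4 weeks: last dose Week 8 = Day 57. Week 14: 99 - 57 = 42 days (36 to 48). Week 24: 169 - 57 = 112 days (102 to 122).

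An ADA test at Week 24 would extend observation by 70 days. This result needs no pharmacokinetic assumption.

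**2. Animal detection rates** (Section 2.3.2)

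- Dosing phase of the 14-week study: 13/35 = 37% (exact 95% CI 21% to 55%).
- Recovery phase: 8/10 = 80% (44% to 97%).

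These are descriptive. The 10 recovery animals may be among the 35, so a test that treats the groups as independent would not be valid and none is relied on. The timing of the recovery samples and the dose mix are not given.

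**3. How much drug might remain**

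The only human input is the accumulation ratio in Section 2.4.2: R = 1.25 to 1.27 for AUC over the dosing interval, cycle 2 against cycle 1, at 1,100 to 1,400 mg every 21 days. Assume one compartment and linear kinetics:

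- R = 1 + exp(-21k), so exp(-21k) = R - 1 and half-life = 21 × ln 2 / -ln(R - 1).
- R = 1.25 gives 10.5 days; R = 1.27 gives 11.1 days. Reading R as a steady-state ratio, 1/(1 - exp(-21k)), gives 9.0 to 9.4 days.
- The share of the last dose's contribution left after d days is 0.5^(d / half-life) = (R - 1)^(d/21).
- Week 14, every 2 weeks: 0.25^(28/21) = 15.7% to 0.27^(28/21) = 17.5%. Every 4 weeks: 0.25^2 = 6.3% to 0.27^2 = 7.3%.
- Week 24, every 2 weeks: 0.16% to 0.22%. Every 4 weeks: 0.06% to 0.09%.

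Because the half-life is an assumption, the range matters more than the point value:

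| Assumed half-life (days) | Week 14, every 2 weeks | Week 14, every 4 weeks |
|---|---|---|
| 3 | 0.16% | 0.01% |
| 4 | 0.8% | 0.07% |
| 6 | 3.9% | 0.8% |
| 8 | 8.8% | 2.6% |
| 10.5 | 15.8% | 6.3% |
| 14 | 25% | 12.5% |
| 21 | 40% | 25% |

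The low end cannot be excluded. Cohort A maintenance is 2 mg/kg, or 140 mg at an assumed 70 kg. The doses behind the accumulation ratio are 8 to 10 times larger (1,100/140 = 7.9; 1,400/140 = 10). Section 2.3.2 reports nonlinear exposure in monkeys at 0.1 to 5 mg/kg, becoming linear once receptor-mediated clearance was saturated, so clearance at low levels may be faster than the ratio implies. Later cohorts may have maintenance doses up to 8 mg/kg, where slower clearance is plausible but not shown.

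**The case against.** The strongest reply is that nothing here shows the Week 14 result to be wrong. A reader might infer from Section 2.3.2 that enough drug is present at Week 14 to hide ADA, that a negative result then cannot be interpreted, and that the reported rate is biased low. The documents do not support that chain.

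- The interference remark is hedged ("may have interfered with detection of ADAs in animals that tested ADA-negative") and concerns high concentrations in monkeys given 10 to 300 mg/kg once weekly.
- A percentage of the last dose is not a concentration, and the assay's drug tolerance is not stated. It may be in the laboratory manual or in the detailed analysis plan that Section 9.3.1 says is provided separately.
- Serum AMB-05X is measured at the same Week 14 visit, so once the tolerance is known a negative result can be read against the concurrent level.
- Week 14 is itself an off-drug sample, so the animal contrast between dosing and recovery does not show that it is too early.

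All of this stands, and it makes the masking argument conditional.

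A reader might also cite the platelet effects and deaths in ADA-positive monkeys (Section 2.3.3) as a safety reason. The same section says these effects are not considered predictive of human risk, that animal immunogenicity predicts human responses poorly, and that it is generally greater than in humans. The events were acute and post-dose, while no dose is planned after Week 10. Nor is re-treatment planned, so an argument from that fails too.

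None of these points touches the simpler gap: an antibody first detectable after Week 14 is not looked for. Poor animal-to-human prediction, if anything, favours measuring human ADA directly, and Section 2.4 summarises no human ADA results.

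**Conclusion.** The gap is real and follows from the sampling schedule alone: ADA that first becomes detectable after Week 14 is missed, although serum is drawn 70 days later. The reported ADA incidence may therefore be too low. By how much cannot be estimated, because the documents give no human ADA rate or time course.

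Masking at Week 14 is a second, conditional reason. If the half-life is 10.5 to 11.1 days (one compartment, linear, carried over from 1,100 to 1,400 mg every 3 weeks), about 16-17% (every 2 weeks) or 6-7% (every 4 weeks) of the last dose's contribution remains at Week 14, against 0.06-0.2% at Week 24. If it is 4 days or less, under 1% remains at Week 14 and masking loses most of its force. It should not be presented as an established bias.

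No sample size, error rate or primary-endpoint result is affected. This is a cheap improvement to a secondary endpoint.

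**What to change.** - Add serum anti-AMB-05X antibody to the existing Week 24 draw in Sections 1.1, 1.3, 7.5 and 8.10. State that it also applies when Visit 10 is done as an early-termination procedure under Section 8.11. This matters most for early stoppers: Section 8.8 (Visit 8 or early termination) has no ADA draw, and a subject who stops before Week 8 may have no last-dose sample either.
- Report ADA incidence as any positive result through Week 24, by cohort and overall.
- Show each ADA result beside the drug level from the same visit and state the assay's drug tolerance, so that negatives obtained above the tolerance can be identified. The drug levels are already planned.

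Cost: up to about 48 extra assays (one per subject), possibly one extra aliquot per subject, and a short protocol amendment. There is no extra visit, procedure or subject. ADA that appears and disappears between Week 14 and Week 24 would still be missed.

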7.6 Blood Sampling

Blood samples will be taken by direct venipuncture. Blood sampling volumes will be limited by the most stringent regulations applicable to a particular site or region. Details on sample collection and processing will be described in a separate laboratory manual.

8 ASSESSMENTS BY STUDY VISIT

The Schedule of Events for this study is provided in [Section 1.3](#).

Refer to [Appendix 5](#) for potential changes to study conduct in the context of COVID-19, including the possibility of remote visits.

8.1 Visit 1 / Screening

After the subject provides signed consent and HIPAA authorization (if applicable), complete the following procedures. If necessary, screening assessments may be performed at more than 1 visit during the 4-week screening period.

- Obtain a 6-digit Subject ID from IWRS.
- Collect demographic information and take medical history.
- Record all concomitant medications, including dose amount and dosing frequency, taken within 4 weeks before Screening.
- Obtain height and weight.
- Measure vital signs (blood pressure, heart rate, temperature, and respiratory rate) with subject in a sitting position after having rested for 5 minutes.
- Conduct a full physical examination.
- Perform a 12-lead ECG.
- Evaluate ROM of the affected joint.
- Administer the following PRO instruments:
 - PROMIS Physical Function Scale
 - Worst Stiffness NRS
 - BPI Short Form
 - EQ-5D-5L
- Collect a urine sample for urinalysis.
- Collect blood samples for HBV, HCV, HIV, TB (QuantiFERON), serum pregnancy test for females of childbearing potential, and clinical laboratory tests (chemistry and hematology).
- Perform MRI. A central radiologist will evaluate MRI scans to assess tumors.
- For subjects whose TGCT diagnosis has not been previously histologically confirmed, a tumor biopsy will be performed during the screening period after the central radiologist has reviewed the subject's screening MRI scan.
- Once test results are obtained, check inclusion/exclusion criteria.

Individuals who successfully complete screening procedures and meet all eligibility criteria will be notified and scheduled for Visit 2 (Baseline). The interval between Visit 1 (Screening) and Visit 2 (Baseline) should not exceed 4 weeks.

For any individual who does not meet eligibility criteria, capture screen failure information, contact IWRS to report screen failure status, and record any changes in concomitant medications and AEs since Screening.

8.2 Visit 2 / Baseline (Day 1)

Approximately 16 to 24 hours before scheduled study drug administration, set up the appropriate number of study drug vials to thaw in the refrigerator according to [Section 6.1.2](#).

8.2.1 Pre-dose Procedures

- Collect a urine sample for a urine pregnancy test for females of childbearing potential and for urinalysis.
- Update any changes in concomitant medications since Visit 1 (Screening).
- Record any AEs that may have occurred since the ICF was signed. AEs that occur before the first dose of study drug will be recorded as such to distinguish them from TEAEs.
- Once test results are obtained, check inclusion/exclusion criteria.
 - Individuals who do not meet eligibility criteria (eg, females of childbearing potential with a positive pregnancy test) will be recorded as screen failures.

If the subject met all inclusion and no exclusion criteria, complete the following procedures:

- Obtain weight.
- Measure vital signs (blood pressure, heart rate, temperature, and respiratory rate) with the subject in a sitting position after having rested for 5 minutes.
- Conduct a full physical examination and document any changes since the previous visit.
- Perform a 12-lead ECG.
- Evaluate ROM of the affected joint.
- Administer the following PRO instruments:
 - PROMIS Physical Function Scale
 - Worst Stiffness NRS
 - BPI Short Form
 - EQ-5D-5L
- Collect blood samples for clinical laboratory tests (chemistry and hematology) and serum PK, CSF1, and anti-AMB-05X antibody (pre-dose sample).
- Optional assessment: collect synovial fluid for PK, CSF1, and anti-AMB-05X antibody.

8.2.2 First Dose and Post-dose Procedures

- Administer study drug via IV infusion.
- Collect blood samples for serum PK and CSF1 within 15 minutes after the end of infusion.
- Monitor the subject for at least 60 minutes post-dose for any adverse reactions, including any infusion-site reactions.

- Schedule the subject for Visit 3 (Week 2).
- Contact IWRs to record the visit.

8.3 Visit 3 (Week 2 ± 2 Days)

If the subject is on an every-2-weeks study drug regimen, set up the appropriate number of study drug vials to thaw in the refrigerator approximately 16 to 24 hours before scheduled study drug administration and according to [Section 6.1.2](#).

For all subjects, complete the following procedures during the visit:

- Record any changes in concomitant medications since the previous visit.
- Record any new AEs that may have occurred since the previous visit and follow up on the status of any existing AEs.
- Obtain weight.
- Measure vital signs (blood pressure, heart rate, temperature, and respiratory rate) with subject in a sitting position after having rested for 5 minutes.
- Collect a urine sample for urinalysis.
- Collect blood samples for clinical laboratory tests (chemistry and hematology).
- Collect blood samples for serum PK and CSF1 (before study drug administration, if applicable for the subject).
- Schedule the next visit with the subject.
- Contact IWRs to record the visit.

If the subject is on an every-2-weeks study drug regimen, administer study drug via IV infusion. Monitor the subject for at least 60 minutes post-dose for any adverse reactions, including any infusion-site reactions.

8.4 Visit 4 (Week 4 ± 2 Days)

Set up the appropriate number of study drug vials to thaw in the refrigerator approximately 16 to 24 hours before scheduled study drug administration and according to [Section 6.1.2](#).

Complete the following procedures during the visit:

- Collect a urine sample for a urine pregnancy test for female subjects of childbearing potential and for urinalysis.
 - Any subject with a positive pregnancy test result must complete ET procedures and will be recorded as ET.
- Record any changes in concomitant medications since the previous visit.
- Record any new AEs that may have occurred since the previous visit and follow up on the status of any existing AEs.
- Obtain weight.

- Measure vital signs (blood pressure, heart rate, temperature, and respiratory rate) with subject in a sitting position after having rested for 5 minutes.
- Collect blood samples for clinical laboratory tests (chemistry and hematology).
- Collect pre-dose blood samples for serum PK, CSF1, and anti-AMB-05X antibody.
- Administer study drug via IV infusion.
- Collect post-dose blood samples for serum PK and CSF1 within 15 minutes after the end of infusion.
- Monitor the subject for at least 60 minutes post-dose for any adverse reactions, including any infusion-site reactions.
- Schedule the next visit with the subject.
- Contact IWRs to record the visit.

8.5 Visit 5 (Week 6 ± 3 Days)

If the subject is on an every-2-weeks study drug regimen, set up the appropriate number of study drug vials to thaw in the refrigerator approximately 16 to 24 hours before scheduled study drug administration and according to [Section 6.1.2](#).

For all subjects, complete the following procedures during the visit:

- Collect a urine sample for urinalysis.
- Record any changes in concomitant medications since the previous visit.
- Record any new AEs that may have occurred since the previous visit and follow up on the status of any existing AEs.
- Obtain weight.
- Measure vital signs (blood pressure, heart rate, temperature, and respiratory rate) with subject in a sitting position after having rested for 5 minutes.
- Conduct a full physical examination and document any changes since the previous physical exam.
- Perform a 12-lead ECG.
- Evaluate ROM of the affected joint.
- Administer the following PRO instruments:
 - PROMIS Physical Function Scale
 - Worst Stiffness NRS
 - BPI Short Form
 - EQ-5D-5L
- Collect blood samples for clinical laboratory tests (chemistry and hematology).
- Collect blood samples for serum PK and CSF1 (before study drug administration, if applicable for the subject).
- Perform MRI. A central radiologist will evaluate MRI scans to assess tumors.

- Schedule the next visit with the subject.
- Contact IWRs to record the visit.

If the subject is on an every-2-weeks study drug regimen, administer study drug via IV infusion. Monitor the subject for at least 60 minutes post-dose for any adverse reactions, including any infusion-site reactions.

